1.0 GENERAL INFORMATION

1.1 Protocol Number and Title of the Study

Protocol No. A19-11184

Protocol Title: A Phase I Study to Evaluate Safety and Tolerability of APR-246 in Combination with Venetoclax and Azacitidine in Patients with Myeloid Malignancies

1.2 Sponsor

Aprea Therapeutics, Inc.

1.3 Monitor

1.4 Signature Authorization

The protocol will be signed by Aprea Therapeutics, Inc.

2.0 BACKGROUND INFORMATION

2.1 Introduction

2.1.1 Acute Myeloid Leukemia

AML is a group of hematopoietic neoplasms characterized by a clonal proliferation of myeloid precursors with a reduced capacity to differentiate into mature cells. AML is the most common type of acute leukemia in adults, with an incidence of over 20,000 cases per year in the United States¹⁻⁴.

Cytogenetic and mutation testing remain critical prognostic tools to assess prognosis and plan induction and post-remission treatment strategies⁵. Testing peripheral blood and bone marrow samples using next generation sequencing (NGS) has developed into a standard of care for determining molecular mutations. Mutations in the tumor suppressor gene *TP53* are found in approximately 20% of patients with AML and are associated with an adverse prognosis. In addition, approximately 80% of patients with *TP53*-mutant AML have a complex karyotype, which also confers an adverse prognosis⁶.

Despite increased understanding of the biology and development of new therapeutic targets, AML treatment remains relatively unchanged, with therapies limited to intensive chemotherapy comprised of cytarabine and anthracycline and non-intensive therapies consisting of a HMA, sometimes incorporating the BCL-2 inhibitor venetoclax. Allogeneic stem cell transplantation is recommended for patients with high risk and relapsed or refractory (R/R) AML who achieve a suitable response and are eligible for SCT.

Non-intensive therapies are utilized to treat patients who are considered ineligible for intensive chemotherapy on the basis of advanced age, comorbidities, and low likelihood of achieving a response based on adverse cytogenetic/molecular features and/or a history of an antecedent hematologic disorder. Non-intensive therapies consist of the HMAs decitabine and azacitidine and low-dose cytarabine (LDAC)⁷⁻¹⁰. Both agents have activity in AML as initial induction therapy and in the relapsed setting^{8,9,11}. Recently, HMAs¹² and LDAC¹³ have been combined with venetoclax in the initial treatment of AML. In addition, HMAs have been combined with venetoclax to treat patients with R/R AML¹⁴.

2.1.2 *TP53* Mutations in Myeloid Malignancies

[figure not shown]
TP53 is a tumor suppressor protein that plays a pivotal role in maintaining genomic stability in response to DNA damage. It is mutated in over half of human cancers^{15,16}, and such mutations represent an important mechanism of resistance to DNA-damaging chemotherapeutic agents^{17,18}. A significant proportion of mutations recurrently target 'hot-spot' codons. They either directly disrupt the DNA-binding domain of *TP53* or cause conformational changes of the *TP53* protein, thus leading to severely impaired *TP53* function.

Mutated *TP53* is predominantly observed in therapy-related AML^{19,20} and/or in patients with complex karyotype (70-80%)²¹. The reported frequency of *TP53* mutations is 5-10% in *de-novo* AML²²⁻²⁴. It has been demonstrated that gain of function mutations in hot spot regions can promote a more aggressive AML²⁵⁻²⁸. In multivariate analysis, the presence of *TP53* mutations predicted for poor overall survival and inferior response to treatment^{27,29-32}.

In a retrospective analysis of 55 patients who received azacitidine therapy for first line treatment of *TP53*-mutant AML, the CR + CRI rate was 21.8%³³. Though the remission rate was not significantly different from patients with wild type *TP53*, the median survival was significantly shorter (7.9 vs 12.6 months, p<.001) for patients with *TP53* mutations. A similar median OS of 7.9 months was observed in patients with *TP53*-mutant AML who received initial therapy with azacitidine³⁴. Regarding patients with *TP53* mutations who received venetoclax with HMAs, the CR/CRI rate was 47%¹². In 10 patients who received venetoclax with LDAC, there were no CRs and 3 patients achieved CRI¹³. Responses in later lines are even poorer¹⁴.

Together, these data highlight the poor outcomes of *TP53*-mutant patients, even with recently approved venetoclax-containing therapies, and the important need for the development of novel therapeutic strategies, particularly in this patient population.

2.2 APR-246

2.3 Venetoclax

Venetoclax is a BCL-2 inhibitor that approved by the U.S. FDA for use in combination with HMAs for the treatment of patients with newly diagnosed AML who are 75 years or older or who have comorbidities that preclude use of intensive induction chemotherapy. Accelerated

approval was granted based on the results of the Phase Ib study with HMAs for patients 65 years or older with treatment-naïve AML, ineligible for intensive chemotherapy by age or comorbidities³⁵. Sixty-seven percent of patients in the study achieved CR or CR with incomplete count recovery (CRI). The median DoR was 11.3 months, and median overall survival was 17.5 months in all patients. It was shown that treatment with venetoclax in combination with an HMA leads to a decrease in oxidative phosphorylation via disruption of electron transport chain in a glutathione-dependent fashion and selective targeting of the leukemia stem cell population³⁶.

Per venetoclax US Prescribing Information (USPI)³⁷ dated May 2020, the most common adverse reactions (≥30%) of any grade in AML patients receiving venetoclax in combination with azacitidine are nausea, diarrhea, constipation, neutropenia, thrombocytopenia, hemorrhage, peripheral edema, vomiting, fatigue, febrile neutropenia, rash, and anemia. Serious adverse reactions were reported in 75% of AML patients receiving venetoclax in combination with azacitidine, with the most frequent serious adverse reactions in ≥5% of patients being febrile neutropenia, pneumonia (excluding fungal), sepsis (excluding fungal), respiratory failure, and multiple organ dysfunction syndrome.

Following multiple doses under fed conditions, maximum plasma concentration of venetoclax are reached 5–8 hours after dose. It is recommended that venetoclax be administered with a meal as food increases the absorption after oral administration. Venetoclax is cleared from systemic circulation via hepatic elimination. The terminal elimination half-life is approximately 26 hours. The pharmacokinetics of venetoclax do not change over time. Venetoclax is predominantly metabolized by CYP3A4/5. CYP3A4 inhibitors and inducers as well as P-gp inhibitors cause clinically relevant drug-drug interactions with venetoclax. For the same reason certain food must be avoided: grapefruit, grapefruit juice, Seville oranges (often used in marmalades), starfruit (CYP3A inhibiting), and St John's wort (CYP3A inducing). Based on their metabolic profiles, a pharmacokinetic drug-drug interaction of venetoclax with APR-246 is considered unlikely.

2.4 Azacitidine

Azacitidine is a nucleoside metabolic inhibitor indicated by the U.S. FDA for the treatment of patients with the following French-American-British (FAB) MDS subtypes: refractory anemia (RA) or refractory anemia with ringed sideroblasts (if accompanied by neutropenia or thrombocytopenia or requiring transfusions), refractory anemia with excess blasts (RAEB), refractory anemia with excess blasts in transformation (RAEB-T), and chronic myelomonocytic leukemia (CMML).

In 2008, azacitidine was approved by the European Medicines Agency (EMA) for the treatment of AML patients with 20–30% bone marrow blasts, older than 64 years and who are ineligible for HSCT. EMA approval of azacitidine was expanded on 30 October 2015 to include AML patients with >30% bone marrow blasts.

The recommended starting dose for the first treatment cycle, for all patients regardless of baseline hematology laboratory values, is 75 mg/m² subcutaneously or intravenously, daily for 7 days. Cycles should be repeated every 28 days. Treatment may be continued as long as the patient derives clinical benefit.

Azacitidine is rapidly absorbed after subcutaneous or IV administration with a V_d of 76 ± 26 L and a half-life of 41 ± 8 minutes. C_{max} is reached after about 30 minutes. Azacitidine and its metabolites are known to be substantially excreted by the kidney, and the risk of adverse reactions to this drug may be greater in patients with impaired renal function. Urinary excretion is the primary route of elimination; the cumulated urinary excretion is 85% of radioactive dose with less than 1% recovered in feces over 3 days.

Azacitidine undergoes spontaneous hydrolysis in aqueous solution and is deaminated by cytidine deamidases, whereas APR-246 is glucuronidated. Drug-drug interaction is not likely although both compounds and their degradation products and metabolites are primarily eliminated by urinary excretion. The pharmacokinetic interaction between APR-246 and azacitidine will be investigated in an ongoing parallel trial.

2.5 Combination of Venetoclax with Azacitidine

Venetoclax has demonstrated synergistic activity in combination with azacitidine in preclinical models³⁸. This relationship was supported by clinical data from a large, multicenter, Phase Ib study (NCT02203773) in elderly patients with treatment-naïve AML, ineligible for intensive chemotherapy¹². Promising efficacy and a tolerable safety profile of this novel combination, with a high CR + CRi rate of 73% in the 400-mg venetoclax in combination with HMA (azacitidine or decitabine) cohort (P=0.35), low early mortality rates, and OS extending beyond 17 months. The median duration of CR + CRi for the venetoclax 400 mg in combination with HMA was 12.5 months (95% CI). Patients with TP53 mutations achieved a CR/CRi rate of 47%^{22,39}. Importantly, the best response of CR + CRi has been attained at median of 1.8 months compared with 3.5 months with azacitidine alone⁴⁰. Response rates were similar between the azacitidine and decitabine cohorts (76% vs 71%, respectively). A Phase III, randomized, double-blind, placebo-controlled study of venetoclax 400 mg combined with azacitidine in treatment-naïve elderly and adult patients with AML ineligible for standard induction therapy is currently underway (NCT02993523) and aims to evaluate the potential impact of venetoclax with azacitidine compared to azacitidine alone

[REDACTED]

2.6 APR-246 Preclinical Studies

2.6.1 Pharmacology and Mode of Action

[REDACTED]

[REDACTED]

A series of 12 horizontal black bars of varying lengths, decreasing in size from top to bottom, followed by a solid black bar at the bottom.

[figure not shown]
A series of eight horizontal black bars of varying heights, creating a stepped or staircase pattern. The bars are arranged vertically, with each subsequent bar being slightly taller than the one below it, starting from a low height and ending at a high height. The bars are set against a white background.

11. **What is the primary purpose of the study?** (check all that apply)

[REDACTED]

2.6.3 Pharmacokinetics and Metabolism in Animals

[REDACTED]

2.7 APR-246 Clinical Studies

113
114
115

[figure not shown]
2.7.1 Phase I/II Study in Solid and Hematological Malignancies

A black and white image showing a series of horizontal bars. The bars are white with black outlines, arranged in a grid pattern. The top row has 10 bars. The second row has 9 bars. The third row has 8 bars. The fourth row has 7 bars. The fifth row has 6 bars. The sixth row has 5 bars. The seventh row has 4 bars. The eighth row has 3 bars. The ninth row has 2 bars. The tenth row has 1 bar. The bottom row is a solid black bar.

[figure not shown]
[figure not shown]
A horizontal bar composed of seven black rectangular segments of varying widths. The segments are arranged in a staggered pattern, with the first segment being the widest and the last segment being the narrowest. There is a small white gap between the second and third segments, and a larger white gap between the third and fourth segments.

2.7.2 Phase I/II Study in *TP53*-Mutant Advanced Ovarian Cancer

113. *Leptothrix* *leptothrix* (L.) *Leptothrix* *leptothrix* (L.) *Leptothrix* *leptothrix* (L.)

[figure not shown]

2.7.3 Phase I/Ib Study in Refractory Hematologic Malignancies

2.7.5 Phase III Multicenter, Randomized, Open Label Study of APR-246 in Combination with Azacitidine

2.7.6 APR-246 CNS Safety Overview

2.8 Dose Rationale for APR-246 in Combination with Venetoclax and/or Azacitidine

[REDACTED]

2.8.1 APR-246 and Azacitidine

[REDACTED]

[REDACTED]

2.8.2 Venetoclax and Azacitidine

[figure not shown]
The doses of venetoclax and azacitidine for patients receiving doublet therapy (APR-246 and venetoclax) or triplet therapy (APR-246, venetoclax and azacitidine) are consistent with the doses recommended in the venetoclax USPI⁴⁸ for patients with AML.

2.8.3 Venetoclax and APR-246

[REDACTED]

A large block of black redacted text, consisting of approximately 20 lines of text that have been completely obscured by black bars.

2.8.4 Expansion Cohorts in Front Line AML

A series of horizontal black bars of varying lengths, likely representing data or text that has been redacted or obscured. The bars are arranged vertically and vary in length, with some being very short and others being quite long, filling most of the vertical space.

2.9.2 Potential Benefits

Patients with *TP53*-mutant myeloid malignancies, including AML, have a poor prognosis and unmet medical need. Azacitidine and venetoclax represent standard of care agents for *TP53*-mutant AML. APR-246 in combination with azacitidine has demonstrated compelling clinical efficacy and a manageable safety profile in patients with *TP53*-mutant MDS/AML, and APR-246 has demonstrated *in vitro* synergy with azacitidine and venetoclax. The purpose of this clinical trial is to define the safety and tolerability of APR-246 in combination with venetoclax and/or azacitidine in patients with *TP53*-mutant AML and to determine preliminary efficacy. Given that *TP53*-mutant MDS and AML patients have a limited life expectancy and lack of effective treatments, the benefit/risk assessment supports the use of APR-246 in this trial.

2.10 Characteristics of a Well-Conducted Trial

The following characteristics of an adequate and well-conducted trial will be implemented:

1. The Investigators will be well qualified by scientific training and experience.
2. Detailed CRFs will be completed for every patient.
3. Requirements for institutional ethics review as set forth by the appropriate Institutional Review Board/Independent Ethics Committee (IRB/IEC), Title 21 Code of Federal Regulations (CFR) Part 56, the European Union Directive 2001/20/EC and its associated Detailed Guidances, European Union GCP Directive 2005/28/EC, the ICH Guideline for GCP, Sections 3 and 4, and the terms of the Declaration of Helsinki

(2013), will be followed.

4. Requirements for informed consent in accordance with institutional guidelines, FDA requirements as specified in Title 21 CFR, Part 50, the European Union Directive 2001/20/EC and its associated Detailed Guidances, European Union GCP Directive 2005/28/EC, the ICH Guideline for GCP, Section 4.8, and the terms of the Declaration of Helsinki (2013), will be followed.
5. Safety data will be recorded and evaluated.
6. Routine monitoring visits will be conducted by the Sponsor's representative to ensure data accuracy.
7. Drug accountability will be strictly maintained.
8. This trial will be conducted according to GCP, the protocol and applicable regulatory requirements.

2.11 Patient Population

This study will enroll adult male and female patients of age ≥ 18 years with documented diagnosis of AML, according to WHO classification, and documented *TP53* mutation, which is not benign or likely benign, who also meet the eligibility requirements of this protocol.

3.0 TRIAL OBJECTIVES AND PURPOSE

Primary objective:

To evaluate the safety and tolerability of administration of APR-246 in combination with venetoclax and/or azacitidine in patients with *TP53*-mutant myeloid malignancies.

Secondary objectives:

1. To assess the clinical activity of APR-246 in combination with venetoclax and/or azacitidine in patients with myeloid malignancies by determination of CR rate.
2. To assess the clinical activity of APR-246 in combination with venetoclax and/or azacitidine in patients with myeloid malignancies by determination of CR plus CRi rate.
3. To assess the clinical activity of APR-246 in combination with venetoclax and/or azacitidine in patients with myeloid malignancies by determination of CR plus CRh rate.
4. To assess the clinical activity of APR-246 in combination with venetoclax and/or azacitidine in patients with myeloid malignancies by determination of ORR.
5. To assess the clinical activity of APR-246 in combination with venetoclax and/or azacitidine in patients with AML by determination of PFS.
6. To assess the clinical activity of APR-246 in combination with venetoclax and/or azacitidine in patients with AML by determination of transition rate to HSCT.
7. To assess the clinical activity of APR-246 in combination with venetoclax and/or azacitidine in patients with AML by determination of OS.

8. To assess clinical activity of APR-246 in combination with venetoclax and/or azacitidine in patients with AML by determining the rate of RBC and/or platelet TI for at least 56 days.
9. To determine the pharmacokinetic profile of APR-246 and venetoclax.

Exploratory objectives:

1. To investigate molecular biomarkers for response prediction and disease monitoring in baseline and serial bone marrow or blood samples.

4.0 TRIAL DESIGN

4.1 Overview of Trial Design

Study treatment may be administered on an outpatient basis. No investigational or commercial agents or therapies other than those described below may be administered with the intent to treat the patient's disease. Hydroxyurea may be used for control of leukocytosis.

The study includes a safety lead-in dose-finding portion followed by expansion portion. During the safety lead-in portion of the study, two cohorts will independently enroll patients following a 3 + 3 design.

Safety lead-in cohort 1 will enroll patients with AML or MDS who have received at least one prior HMA regimen for MDS. These patients will receive APR-246 at 4.5 g/day on days 1 – 4 of each 28-day cycle administered concurrently with venetoclax that is given orally at the dose of 400 mg daily once the ramp-up phase is completed. If a prophylactic antifungal agent is administered concurrently, the daily dose of venetoclax should be determined based on institutional practice and current prescribing information for venetoclax. Safety lead-in cohort 2 will enroll patients with previously untreated *TP53*-mutant AML (prior MDS is allowed, but not treatment with HMA), who will receive APR-246 at 4.5 g/day on days 1 – 4 administered concurrently with venetoclax given orally at the dose of 400 mg daily and with azacitidine at the standard dose of 75 mg/m² over 7 consecutive days as a subcutaneous injection or IV infusion on days 1 – 7 of each 28-day cycle.

Each cohort will enroll up to 6 patients. DLT will be assessed after three patients have been enrolled in respective cohort and the last enrolled patient has completed the 4-week safety assessment period (i.e., one cycle of combination regimen). A patient that discontinues therapy during Cycle 1 without DLT is considered evaluable for the purpose of safety only if at least 80% of scheduled doses of APR-246 in combination with venetoclax and/or azacitidine were administered in the first cycle. At the first dose level of 4.5 g/day of APR-246, if ≤1 patient out of 3 experiences a DLT, 3 additional patients will be enrolled. If ≤1 patient out of 6 experiences DLT, the dose level (4.5 g/day of APR-246) will be deemed the RP2D for that cohort. If ≥2 patients out of the total 3–6 patients in the cohort experience DLT, the study will continue enrollment at Dose Level -1 (4.0 g/day of APR-246). If ≤1 patient out of 6 experiences DLT at this dose level, the dose level (4.0 g/day of APR-246) will be deemed the

RP2D for that cohort. If ≥ 2 patients out of the total 3 – 6 patients at that dose level experience DLT, the study will continue enrollment at Dose Level -2 (3.5 g/day of APR-246). If ≤ 1 patient out of 6 experiences DLT at this dose level, the dose level (3.5 g/day of APR-246) will be deemed the RP2D for that cohort. If ≥ 2 patients out of the total 3–6 patients at this dose level experience DLT, no additional patients will be enrolled at this dose. The trial will be halted, and the DRT will consider potential future dosing modifications.

Table 2. APR-246 Dose Levels

Dose Modification	APR-246 Dose
Starting Dose Level (DL)	APR-246 4.5 g/day 1.5 g (for first 45 minutes) + 3.0 g (for 5 hours 15 minutes)
Dose Level Reduction -1 (DL-1)	APR-246 4.0 g/day 1.33 g (for first 45 minutes) + 2.67 g (for 5 hours 15 minutes)
Dose Level Reduction -2 (DL-2)	APR-246 3.5 g/day 1.17 g (for first 45 minutes) + 2.33 g (for 5 hours 15 minutes)

The expansion portion will begin once the RP2D of APR-246 in combination with venetoclax and/or azacitidine have been determined in order to assess the antitumor activity of these combinations. Approximately 70 patients will be enrolled in up to five cohorts, as outlined in [Table 3](#):

Table 3. Study Treatment and Prior Therapy by Cohort

Cohort	Disease	Study Treatment	Prior Therapy Permitted						
			VEN	HMA	LDAC	APR-246	SCT	IC	
Safety Lead-In Cohorts									
Cohort 1	F/L AML	APR-246 + VEN	no	≥ 1 prior for MDS required	no	no	yes for MDS	no	
Cohort 2	F/L AML	APR-246 + VEN + AZA	no	no	no	no	no	no	
Expansion Cohorts									
Cohort 1	F/L AML	APR-246 + VEN	no	yes for MDS	no	no	yes for MDS	no	

Cohort 2	F/L AML	APR-246 + VEN + AZA	no	no	no	no	no	no
Cohort 3	R/R AML	APR-246 + VEN	yes	yes	Yes	yes for MDS	yes	yes
Cohort 4	R/R AML	APR-246 + VEN + AZA	yes	no	no	yes for MDS	yes	≤ 1 prior
Cohort 5	F/L AML	APR-246 + AZA	no	no	no	no	no	no

Abbreviations: AZA = azacitidine; F/L = front line; HMA = hypomethylating agent; IC = intensive chemotherapy; LDAC = low-dose cytarabine; MDS = myelodysplastic syndrome; R/R = refractory or relapsed; SCT = stem cell transplant; VEN = venetoclax

Cytopenia and related adverse events (thrombocytopenia, anemia, neutropenia, and febrile neutropenia) are common in patients with AML, particularly in patients with baseline neutropenia or those with secondary AML.

For patients receiving venetoclax in combination with azacitidine, in a case of CRi or a morphologic leukemia-free bone marrow (MLFS) after completion of Cycle 1, administration of venetoclax and APR-246 may be interrupted to allow for ANC recovery from Day 29 until ANC $\geq 0.5 \times 10^9/L$. Blood counts can be assessed within 4 weeks of bone marrow biopsy for response assessments. Cycle 2 administration of azacitidine will also be delayed until ANC $\geq 0.5 \times 10^9/L$. Both venetoclax, azacitidine, and APR-246 will resume on the same day after the interruption. If a patient presents with new onset Grade 4 neutropenia for more than 1 week during subsequent cycles, unless it is thought to be due to the underlying disease, venetoclax dosing may be interrupted until ANC is $\geq 0.5 \times 10^9/L$. For subjects in CR/CRi who required interruption or delay of study drug administration for cytopenia (neutropenia or thrombocytopenia) venetoclax may be administered for 14-21 days out of 28 days during each of the subsequent cycles.

If hematologic recovery is achieved within 14 days after completion of the cycle, the duration of venetoclax is reduced to 21 days of the cycle. If a 25% increase has not been achieved within 14 days after the completion of a cycle, azacitidine dose adjustment can be made based on bone marrow cellularity. In the setting of bone marrow hypocellularity, the dose of azacitidine in the next treatment cycle should be reduced to 50% for 15-50% hypocellularity and to 33% for <15% hypocellularity.

In each portion of the study, patients may continue treatment as long as toxicity remains acceptable and the patient has not withdrawn consent. Response and progressive disease will be assessed based on the IWG AML response criteria ([APPENDIX I](#)) after every treatment cycle the first year, then every two cycles thereafter.

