6.1.3 Azacitidine

Azacitidine is given at the standard dose of 75 mg/m² subcutaneously or intravenously over 7 consecutive days, Days 1-7. On Days 1-4 azacitidine is administered immediately after the APR-246 infusion. SC method is preferred but IV is allowed at the Investigator's discretion. The same route should be maintained over the 7-day treatment period (whichever route is used on Day 1, the other days should follow the same route of administration). Detailed

instructions on preparation and administration can be found in the Pharmacy Binder, current package insert, and in Section [6.2](#), below. The administration of azacitidine may be interrupted by up to 3 days to account for institutional administration practices and policies in addition to holidays.

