6.1.4 Dose-Limiting Toxicity

An event will be considered a DLT per NCI CTCAE version 5.0 criteria if it occurs within 4-week safety assessment period (Cycle 1 of study treatment) and meets at least one of the criteria below:

- Absolute neutrophil count (ANC) not recovering to $>0.5 \times 10^9/L$ and/or platelets not recovering to $>25 \times 10^9/L$ by day 42 of study treatment in the absence of active leukemia/myelodysplasia;
- Grade ≥ 3 nausea/vomiting/diarrhea or CNS toxicity that does not resolve to Grade ≤ 1 within 7 days despite treatment interruption and maximum medical therapy;
- Treatment-related non-hematological Grade ≥ 3 toxicity that does not resolve to Grade ≤ 1 .

A DLT will be considered related to the study treatment unless there is a clear, alternative explanation for the AE. A \geq Grade 3 metabolic or electrolyte abnormalities that is not clinically significant and is adequately controlled within 72 hours is not to be considered DLT. A tumor lysis syndrome that responds to therapy and resolves within 72 hours is not to be considered DLT.

Additionally, AEs that meet the above criteria, but occur after the DLT evaluation period will not be defined as DLTs, but will be reported as AEs/Serious Adverse Events (SAEs) and will be reviewed across all cohorts during the study to help determine the AE profile. A patient

that discontinues therapy during Cycle 1 without DLT is considered evaluable for the purpose of safety only if at least 80% of doses of APR-246 in combination with venetoclax with and without azacitidine were administered in the first cycle.

Patients who are tolerating APR-246 in combination with venetoclax and/or azacitidine, will not have to discontinue dosing prematurely due to the occurrence of DLTs in another patient in the same cohort, unless decided by the DRT. If requested by the Investigator, depending on the nature of the DLT and patient status, the DRT and the Sponsor may allow a patient to continue with study treatment at a reduced dose.

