6.2 Dose Interruptions/Withholding

Study treatment may be withheld from a patient based on the Investigator's decision in the event of intercurrent illness, AE, administrative reasons, or other reasons. If the patient's condition subsequently improves, or the situation that resulted in withholding study drug rectifies itself, the Investigator may resume dosing as soon as possible, unless the delay is more than 4 weeks.

Dosing should be delayed for any DLT-equivalent toxicity and possible NCI CTCAE > Grade 2 AEs considered related to study medication. At the Investigator's discretion, dosing may recommence when the toxicity has resolved to Grade 2 or less. Immune-related reactions or allergy should resolve to \leq Grade 1.

Treatment will be discontinued if a TEAE has not resolved (to acceptable grade) after \leq 4 weeks.

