6.3.6 Management of Neutropenia with or without Fever

Monitor complete blood counts at the time of study enrollment and throughout the course of study treatment. Supportive measures such as antimicrobials for prophylaxis or in the setting of prolonged myelosuppression, and/or at the first signs of infection are recommended to reduce the risk of a serious or severe infection that may lead to a fatal outcome in the setting of neutropenia with or without fever (see Section 6.3.5).

Myeloid growth factors may be used in the setting of severe or prolonged neutropenia. Refer to Section 6.4 Concomitant Treatment, for a description of drugs that are not allowed to be used while a patient is on study treatment.

Please refer to Section 6.2 Dose Interruption/Withholding for guidance on APR-246 dose modification in the setting neutropenia with or without fever.

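### Section 4.1 ties azacitidine reduction to marrow cellularity but prints the bands as percent hypocellularity, so the literal rule runs backwards and gives the emptiest marrows no stated dose

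*Combined protocol and SAP*

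**What the plan says.** The rule is in section 4.1, Overview of Trial Design, in the paragraph after Table 3 that deals with haematologic recovery. It has three parts.

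- Trigger: "If a 25% increase has not been achieved within 14 days after the completion of a cycle".
- Basis: if the trigger is met, "azacitidine dose adjustment can be made based on bone marrow cellularity".
- Amount: "In the setting of bone marrow hypocellularity, the dose of azacitidine in the next treatment cycle should be reduced", and the sentence then gives the bands: "reduced to 50% for 15-50% hypocellularity and to 33% for <15% hypocellularity".

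The dose being reduced is set in section 6.1.3: "Azacitidine is given at the standard dose of 75 mg/m² subcutaneously or intravenously over 7 consecutive days".

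**The concern.** The basis and the amount are in adjacent sentences but use opposite scales. Cellularity falls as the marrow empties, whereas a percentage of hypocellularity would rise. The bands follow the pattern expected of a cellularity scale, with the smaller percentage paired with the deeper cut, but they are labelled with the opposite quantity.

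This is an operative threshold for a cytotoxic drug in a multicentre trial. A site applying the printed words would find no amount for the patients with the emptiest marrows, for whom the rule evidently exists. It would also find the largest cut attached to the marrow nearest to normal. What is at stake is patient safety and consistent azacitidine dosing from Cycle 2 onward. No error rate or analysis is involved.

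**Working it through.** **Inputs.** The full dose is 75 mg/m² daily for 7 days (section 6.1.3), so 75 × 7 = 525 mg/m² per cycle. The bands and fractions come from section 4.1. One assumption is needed that the documents do not supply: hypocellularity *h* = 100 − cellularity *c*, both in percent.

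**Step 1: the dose in each band.**

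- 50%: 0.50 × 75 = 37.5 mg/m² per day; × 7 = 262.5 mg/m² per cycle.
- 33%: 0.33 × 75 = 24.75 mg/m² per day; × 7 = 173.25 mg/m² per cycle.
- Difference: 37.5 − 24.75 = 12.75 mg/m² per day; × 7 = 89.25 mg/m² per cycle; 12.75 / 75 = 17% of the standard dose.

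**Step 2: the rule under each reading.** Literally, *h* < 15 gives 33%, 15 ≤ *h* ≤ 50 gives 50%, and *h* > 50 gives a reduction with no amount. Read as cellularity, *c* < 15 gives 33% and 15 ≤ *c* ≤ 50 gives 50%.

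| Cellularity *c* | Literal wording | Bands read as cellularity |
|---|---|---|
| Below 15% | Reduce, amount not stated | 33% |
| 15% to below 50% | Reduce, amount not stated | 50% |
| Exactly 50% | 50% | 50% |
| Above 50%, up to 85% | 50% | No cut from this rule |
| Above 85% | 33% | No cut from this rule |

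The literal column is in the wrong order: the fullest marrows have the lowest stated dose. The cellularity column is in the right order and gives an amount for every marrow at or below 50%.

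**Step 3: the extent of the gap.** There are 51 whole-number values of *c* from 0 to 50, and the cellularity reading gives an amount for all of them. The literal reading gives none for *c* = 0 to 49, which is 50 of the 51. The two readings agree only at *c* = 50. An unstated amount means that the size of the cut is left open. It does not mean full dose.

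**Step 4: whether another section corrects it.**

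- Section 6.2 works by toxicity grade ("dosing may recommence when the toxicity has resolved to Grade 2 or less") and has no cellularity criterion.
- Section 6.3.6 sends the reader back to 6.2, and only "for guidance on APR-246 dose modification in the setting neutropenia with or without fever".
- Section 6.3.9, on azacitidine adjustments, covers missed doses, bicarbonate and renal changes, then refers to the prescribing information. It does not restate the bands.
- Footnote k to the study calendar (section 7.1) and section 7.2.2.4 mention hypocellularity without a percentage, and only for holding and restarting venetoclax.

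**Step 5: effect on dose finding.** The cut applies to the next cycle. The trigger needs 14 days after a 28-day cycle, so for Cycle 1 it is reached at day 28 + 14 = 42. That is also the last day for the count-recovery criterion in section 6.1.4. An azacitidine reduction under this rule therefore comes too late to alter the Cycle 1 assessment of dose-limiting toxicity.

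**The case against.** The best case against is that the literal reading defeats itself. It needs a scale that the documents never define, and on that scale the lowest band is a marrow more than 85% cellular, in a sentence confined to hypocellular marrows. The sentence before names cellularity. A haematologist would take the bands as cellularity measurements in a hypocellular marrow, and the wording would then be loose rather than wrong. Much of this stands: the intent is probably recoverable. It does not make the printed threshold correct, because the reader still has to replace a word with its opposite.

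The 17% figure can also be challenged. As the table shows, no marrow gets 33% under one reading and 50% under the other. The objection is right that the figure measures the spacing between the bands and not any patient's dosing error. Likewise, 50 of 51 counts values on a scale, not patients.

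The decision to adjust is permissive, and section 6.3.9 points to the label. However, once an investigator adjusts, section 4.1 says what the amount should be, and the protocol does not say whether 4.1 or the label governs. What the label contains cannot be judged from these documents. The Medical Monitor discussion required when venetoclax is held and restarted for a hypocellular marrow makes an uncorrected error less likely at that point, but it does not define azacitidine bands.

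Scope is a fair caveat too. The paragraph before the rule concerns patients on venetoclax with azacitidine, so it is unclear whether the rule reaches expansion Cohort 5 (APR-246 plus azacitidine). Cohorts 1 and 3 receive no azacitidine.

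**Conclusion.** The concern holds. As written, section 4.1 states an azacitidine threshold in the wrong unit. Taken literally, with hypocellularity as 100 minus cellularity, the order of the cuts is reversed and every marrow below 50% cellularity is left without a stated amount. The stated amounts are 24.75 and 37.5 mg/m² per day. How many patients would meet the rule is not given in the documents, and inconsistent dosing between sites is a possibility, not a demonstrated outcome. The recommended Phase II dose, sample size and planned analyses are untouched. The wording should be corrected because it is a dosing instruction that no other section puts right.

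**What to change.** In section 4.1, change *hypocellularity* to *cellularity* in both bands, so that azacitidine goes to 50% of dose at 15-50% cellularity and to 33% of dose below 15%. The clinical team should confirm that this is what was intended.

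In the same edit, as a secondary clarification, state which blood count the 25% increase refers to and the value it is measured from. The text gives neither, and both are for the clinical team to set.

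The cost is one word changed twice and a short phrase in the sentence before. Sample size, visits and data collection do not change.
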